Temperature ^f		Measure and record temperature three times daily until afebrile for 14 days, then once daily in the evening until afebrile for 28 days							
Pulse oximetry ^f	Х	Twice daily through day 15			Thrice weekly through day 29				
Weight	Х								Х
Questionnaire and diary	Х	Every evening days 2-28; days 1, 3, 5 weekly thereafter ^g							
ECG ^h	Х			Х	Х		Х		
Nasal mid-turbinate (NMT) swab for SAR-CoV-2 PCR ⁱ	Х			Х	Х		Х		Х
CBC, biochem profile ^j , D-dimer, INR, PTT				Х	Х		Х		Х
CRP, D-dimer, troponin, ferritin	Х			Х	Х		Х		Х
Serum IgG and IgM antibodies to SARS-CoV-2	Х							С	Х
Alpha-1-antitrypsin and G6PD testing								Ck	X ^k
Study medication		<							
Adverse events ^I			Х	Х	X	Х	Х	Х	Х
Concomitant medications	Х		Х	Х	Х	Х	Х	Х	Х

Abbreviations: BL: Baseline; EOS: end of study; EOT: end of treatment

^aEnd of treatment visit, regardless of actual study day. Should generally be day 15, the day AFTER last dose of study medication.

^bEnd of study visit: generally day 57±4 from start of treatment, regardless of duration of treatment. If patient discontinues study participation prior to then, end of study procedures should be carried out, if possible, at the time of discontinuation from study, even if earlier than day 53.

^cType of contact/location: F: in facility: emergency department, clinic, COVID-19 special facility; H: home visit; H/F: option for either home or facility visit; T: televisit, either phone or video. Note: additional televisits may be arranged as needed. If patient returns to medical facility for outpatient visit, if possible, relevant procedures and tests should be performed at that time.

At all clinic and home health visits, temperature, pulse, respiratory rate, blood pressure, pulse oximetry and ECG measurements will be performed. Home health staff will obtain all vital signs independently of patient measurements, to verify that data are being collected accurately.

^dWithin 3 days prior to planned start of treatment: initial procedures include signing informed consent, review of medical history, review of documentation of COVID-19 disease and source/exposure, if available, height (measured or per patient), pregnancy test for women of childbearing potential, as detailed in section 5.2. When feasible, BL and day 1 procedures, i.e., start of treatment, should be completed on the same day.

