ePhysical examination: physical examination of pertinent systems at baseline, then interim examinations on day 1 of week 2, within 72 h of discontinuation of study medication, study day 29 and within last week of follow-up period. Baseline physical is mandatory for study participation. At each physical examination, a full set of vital signs (temperature, pulse, respiratory rate, blood pressure, and oxygen saturation) will be obtained by the examiner. If one or more on-study visits is not feasible, document in CRF.

The patient will be provided with an electronic thermometer and instructed to measure and record temperature three times daily until afebrile (<38.0°C) for 14 days. Temperature should be measured within an hour of getting up in the morning, between 4-7 pm and within an hour of bedtime each day. Additional temperature readings may be taken at patient initiative or at the instruction of the investigator.

Oxygen saturation will be measured by patients twice daily for the first 2 weeks of study and then three times weekly for the next two weeks. During the first two weeks of study, oxygen saturation should be measured within an hour of arising and within an hour of bedtime, in coordination with the morning and evening temperature readings. After that, oxygen saturation should be measured in the evening, at the time of the evening temperature reading if temperature is still being measured or at the time the patient completes the symptom questionnaire. Additional pulse oximetry readings may be performed at the request of the investigator.

⁹When baseline day = day 1, the patient should not repeat the questionnaire in the evening that day. After day 28 of the study, if a patient does not complete the questionnaire on an assigned day (days 1, 3 and 5 of each week), he or she should complete it during the usual timeframe, 7:00-11:59 pm, on the following day.

^hElectrocardiogram: full 12-lead ECG at baseline visit. At baseline visit and additional days noted, 6-lead ECG is to be performed, either by clinic or home health staff.

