## 13. Analysis of Secondary Efficacy Endpoints

Analysis population: Analysis will be performed using the mITT and PP populations.

Analysis will be performed not only of symptom resolution and occurrence of new symptoms in aggregate, but also by individual symptoms assessed by investigators as related to COVID-19. This includes both the symptoms in the questionnaire and additional, less common symptoms which are recorded on the AE reports but attributed to COVID-19.

Items 1, 2, and 4 below are first-tier secondary objectives, to be analyzed initially. Items 3, and 5 are second tier objectives, which may be reported subsequently. Comparison between active treatment and placebo of the following secondary efficacy endpoints will be performed:

- 1) Incidence of hospitalization or death: the primary assessment of this endpoint will be among patients in the high risk group. This has been defined preliminarily above. The group may be redefined and recruitment for part B restricted based on analysis at the end of part A.
  Specific COVID-19 symptoms resulting in hospitalization will be tabulated by SOC, PT and severity. Depending on the number of patients hospitalized, this may be shown either as a table or listing.
  - Specific main COVID-19 symptoms resulting in death will be listed per patient.
- 2) The proportion of patients who are PCR-negative at each time point assessed, days 8, 15, 29 and 57 from the start of treatment (landmark analysis);
- 3) Time to resolution of individual disease-related symptoms present at baseline; COVID-19 symptoms, derived from the symptom questionnaires and those events entered as related to COVID-19 on the AE tables will be summarized as well using MedDRA classification by SOC, PT and severity as new COVID-19 symptoms and those worsening on study by at least one grade
- 4) Development of new disease-related symptoms or pneumonia on study;
- 5) Changes in laboratory markers of disease severity, i.e., oxygen saturation, CRP, lymphocyte count and D-dimer levels, from baseline to time points at which these are measured on study.

The time frame for all endpoints unless otherwise stated is from Day 1 (day of first dose of study medication) through study Day 57. The time to event endpoints will be analyzed using the methods described for the primary endpoint above.

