Binary (Yes/No) endpoints (i.e., development of pneumonia diagnosed clinically, hospitalization and mortality) will be summarized using counts and percentages for each group. A 95% confidence interval will be constructed for each proportion. For endpoints other than mortality, (e.g, development of new

Study: RHB-107-01 Page 21 of 28

disease-related symptom on study), analysis will treat death before the event of interest as the most unfavorable possible outcome for this endpoint. Additional rules for handling missing data will be determined during blind review of the data and documented prior to unblinding.

Changes from baseline in laboratory markers (continuous variables) will be summarized by descriptive statistics. For oxygen saturation, which is measured twice daily throughout the study period, patterns will be presented visually. The median value for each subject from the preceding week will be used (e.g., for the Day 8, the median SpO2 value for Days 2-8 will be used). The daily SpO2 will be the subject's median of the 14 values collected (morning and evening). The morning and evening SpO2 will be the median of the 7 values at that time of day. Descriptive tables will be done for Days 1, 15, 22, 29, 36, 43, 50, 57.

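### SAP section 13 assumes twice-daily oxygen-saturation readings to day 57; on the protocol's schedule only day 15 of its eight table days can be built as specified, and day 8 is left off the list

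*SAP*

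**What the plan says.** SAP section 13 introduces the oxygen-saturation analysis with "For oxygen saturation, which is measured twice daily throughout the study period, patterns will be presented visually". Each subject's value is the median over the preceding week, illustrated by "e.g., for the Day 8, the median SpO2 value for Days 2-8 will be used". The counts are then given explicitly: "The daily SpO2 will be the subject's median of the 14 values collected (morning and evening") and "The morning and evening SpO2 will be the median of the 7 values at that time of day". The list of table days follows: "Descriptive tables will be done for Days 1, 15, 22, 29, 36, 43, 50, 57". The same section sets the general time frame for endpoints as running "through study Day 57".

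The protocol schedules something different. The pulse oximetry row of Table 1 begins "Twice daily through day 15" and then drops to three readings a week, ending at day 29. The notes to Table 1 agree: "Oxygen saturation will be measured by patients twice daily for the first 2 weeks of study and then three times weekly" for two further weeks. They place those later readings in the evening. Separately, the notes have staff record oxygen saturation at clinic and home visits and at each physical examination, which Table 1 places at baseline and days 8, 15, 29 and 57.

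SAP section 1 names Amendment 4 of 15 June 2021 as its source protocol, and that is the version carrying this schedule.

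**The concern.** The SAP describes a data stream that the protocol does not collect, and its summary rule depends on that description. A programmer working from section 13 would have table shells for days with no scheduled reading, and morning medians for weeks with evening readings only. There would be no shell for the first on-treatment week, where the data are complete.

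Oxygen saturation is a named secondary severity marker and is among the items in the part A DSMB review. If the mismatch is left, someone must decide after the fact what to put in those tables, and the SAP gives no minimum number of readings to guide that decision.

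**Working it through.** **Inputs**

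- SAP section 13: a 7-day window ending on the table day, two readings a day, table days 1, 15, 22, 29, 36, 43, 50 and 57.
- Protocol Table 1 and its notes: home readings twice daily through day 15, then three evenings a week through day 29; staff readings at baseline and days 8, 15, 29 and 57.

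**The SAP's own figure.** 7 days × 2 readings = 14 per window, or 7 morning and 7 evening. This reproduces.

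**Same count on the protocol schedule.** For table day D, count the scheduled home readings in days D−6 to D.

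| Day | Window | Morning | Evening | Home total | Staff reading in window (nominal day) | On SAP table list |
|---|---|---|---|---|---|---|
| 1 | day 1 only | 1 | 1 | 2 | baseline | yes |
| 8 | 2–8 | 7 | 7 | 14 | day 8 | **no** |
| 15 | 9–15 | 7 | 7 | 14 | day 15 | yes |
| 22 | 16–22 | 0 | about 3 | about 3 | none | yes |
| 29 | 23–29 | 0 | about 3 | about 3 | day 29 | yes |
| 36 | 30–36 | 0 | 0 | 0 | none | yes |
| 43 | 37–43 | 0 | 0 | 0 | none | yes |
| 50 | 44–50 | 0 | 0 | 0 | none | yes |
| 57 | 51–57 | 0 | 0 | 0 | day 57 | yes |

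**Tally of the eight listed days**

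- One (day 15) meets the 14-reading definition.
- One (day 1) has no preceding on-study week.
- Two (days 22 and 29) support an evening median of about three values.
- One (day 57) has a single staff value.
- Three (days 36, 43 and 50) have no scheduled source. Days 22 and 43 are televisits in Table 1, and days 36 and 50 have no visit.

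**Overall volume.** The SAP's description implies 57 × 2 = 114 home readings per patient. The protocol schedules about 15 × 2 + 2 × 3 = 36, and 36/114 = 32%.

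**Sensitivity to wording**

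- If the first two weeks are taken to end at day 14 rather than day 15, the day 15 window holds 6 × 2 = 12 readings plus 3/7 of an evening reading, about 12.4. No listed day would then reach 14.
- If home readings end at day 28 rather than day 29, the day 29 window holds 6 × 3/7 = 2.6 evening readings.
- The day 29 visit has a window of ±4 days, so it may fall as late as day 33, inside the day 36 window. A stray staff value could appear there, but not by design.

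None of these changes the picture.

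**The case against.** The best reply is that 14 and 7 describe the counts expected, not a minimum. The operative rule is the median over the preceding week, which can be taken over whatever readings exist. That has force. A reader might infer that most of the tables cannot be produced at all, and the documents do not support that. Days 22 and 29 can show an evening median and day 57 a staff value. What fails is production as specified. Nor does oxygen-saturation measurement stop at day 29; only the home readings do.

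Three other strong readings go too far:

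- **The week 1 comparison is lost.** It is not. Section 13 defines the day 8 median and promises a visual display, and the endpoint covers change from baseline to the measured time points. One entry is missing from a table list, probably by oversight.
- **The late tables would show an unrepresentative group enrolled before Amendment 4.** Protocol section 1.3 says intensive vital-sign monitoring was being cut back after experience with the first patients, so some may have later readings. The documents give neither the previous oximetry schedule nor the number of such patients, and nothing on whether they differ.
- **The DSMB's choice of dose is exposed.** Protocol section 4.8 and SAP section 7 say the pharmacodynamic markers, oxygen saturation among them, are analysed but do not decide dosing.

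Other defences fail. The clause giving the SAP precedence cannot create readings that nobody was asked to take. Section 18 lists only the antipyretic change as a departure from the protocol, and the section 20 appendix does not mention oximetry. Leaving missing-data rules to the blinded review does not help, because these readings are unscheduled rather than missing, and SAP section 4.1 rules out imputation in general.

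**Conclusion.** The point holds, as a minor correction. The frequency stated in SAP section 13 contradicts the protocol version on which the SAP is built. One of the eight listed table days can be built to the stated definition, three have no scheduled reading, and the one other fully populated week (day 8) is omitted.

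The count assumes that patients follow the Amendment 4 schedule, that three readings a week means about three per 7-day window, and that visits occur on their nominal days. Extra readings at the investigator's request are allowed but cannot be planned on.

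The consequence is limited. Part A efficacy analysis is descriptive, laboratory markers including oxygen saturation are second tier in SAP sections 2.2 and 13, and part B is to have its own SAP. No test, primary endpoint or dose decision depends on these tables.

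**What to change.** Amend SAP section 13 as follows:

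- State the frequency as scheduled in Amendment 4.
- Day 1: report the baseline value.
- Days 8 and 15: median of up to 14 readings, with the morning and evening split. This adds day 8 to the list.
- Days 22 and 29: median of the available evening readings, with a stated minimum count and no morning median. Because day 15 pools morning and evening, show its evening median beside these so that like is compared with like.
- Day 57: the single staff reading, labelled as such.
- Days 36, 43 and 50: drop them, or label them as covering only patients who happen to have readings, and show the number contributing. State how any patients monitored under a previous protocol version are handled.

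The cost is SAP wording and table shells. No data collection changes. The same text should be corrected before it is carried into the part B SAP.

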Because a) no oral therapy has demonstrated efficacy in treatment of COVID-19, and b) the existing treatments approved for outpatient use under EUA are antibody combinations indicated only for high risk patients and which require availability of facility for infusion therapy, use of a placebo comparator appears justified in the outpatient population in areas in which the antibodies are not available. In addition, many patients opt not to receive antibody infusions despite their availability. Therefore, patients in part B of the study will be stratified and outcomes will be analyzed according to antibody use. Two thirds of patients entered in part A of the study will receive active drug, and in part B, 60% will receive active drug. Randomization 3:2 in part B will provide an incentive for participation in the study: patients will have a 50% greater probability of receiving active drug than placebo. This also provides a larger sample size for evaluation of safety than a 1:1 randomization. Yet the shift from 1:1 to 3:2 randomization increases the overall sample size by less than 10%.

In part A of the study, upamostat will be administered at a dose of either 200 or 400 mg daily. While both dose levels have been tolerated well in oncology studies, it appears

prudent to test two dose levels in this new population. If both are tolerated similarly, the higher dose will be used in part B of the study. If there are differences in tolerability, absent clinically significant differences in efficacy, the lower dose will be used in part B.

As an early indication of pharmacologic activity, six parameters found to be associated with severity and outcome of COVID-19 disease will be assessed at multiple time points during the study: oxygen saturation, C-reactive protein, lymphocyte counts, D-dimer, troponin and ferritin levels. The primarily pharmacodynamic parameters, CRP, troponin and ferritin, will be followed only in territories in which they are readily available through a central lab which can standardize the results across sites. Those analytes which are also safety parameters, oxygen saturation, D-dimer and lymphocyte counts, will be followed in all patients.

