## 7. Data and Safety Monitoring Board Meeting Scope and Time Point

A data and safety monitoring board (DSMB) will be convened for oversight of the study. A DSMB charter is maintained as a separate document.

**Preliminary review**: The DSMB will be informed by the Sponsor on an ongoing basis of each patient whose study medication dose is reduced or discontinued due to toxicity. DSMB members may request an early review of all patients if warranted by the type, severity or frequency of toxicities resulting in dose reduction or drug discontinuation.

Study: RHB-107-01 Part A Statistical Analysis Plan (Version 2.0) **Initial full review**: The DSMB will review data after the first 60 patients have completed treatment and follow-up (part A), with regard to the following:

- a) Adverse events requiring dose modification or discontinuation of treatment overall and those considered at least possibly related to study medication;
- b) Serious adverse events deemed at least possibly related to study medication;
- c) Serious adverse events of any cause;
- d) Exacerbation of COVID-19 disease, including hospitalization;
- e) Effect of treatment on oxygen saturation, C-reactive protein, lymphocyte count and D-dimer (pharmacodynamic markers);
- f) Additional efficacy parameters available at that time, including time to sustained recovery, as defined above.

In addition to the safety data, proportions of subjects screened, enrolled, and length of follow-up will be provided by site for the Enrolled Population. Screening failure reasons will be summarized. Furthermore, subject disposition based on the Randomized Analysis Population, including subject status. Dose administration status overall and by treatment arm will be provided for the Safety Population.

Baseline information, demographics, treatment status, primary reason for early termination, and baseline laboratory values will be tabulated and summarized for the Safety Population.

A statistically significant difference in any of these parameters is unlikely with a limited early data set. However, the DSMB in conjunction with the sponsor will determine using their clinical judgement if, based on the safety profile of the two active arms, the tolerability is substantially lower at 400 mg as compared to 200 mg daily.

- A. If the DSMB determines that safety of both dose levels is similar, accrual in part B will proceed with the 400 mg daily schedule.

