#### 16.2 Other Parameters

The results from physical examination will be presented in the subject data listings. Vital signs and physical findings will be shown in listings, but no calculations or study report tables will be generated. Findings on physical examination, including vital signs, which constitute clinically significant changes will be listed as adverse events. This will be done in the second-tier analysis.

Supplemental oxygen and ventilator use will be tabulated by treatment arm and overall population. This is applicable only for hospitalized patients; the relevant information will be obtained from hospital records of these patients. This will be prioritized in the first-tier analysis.

The result of rRT-PCR will be tabulated by positive or negative and, for positives, by viral load at each time point assessed and over time. This will be prioritized in the first-tier analysis.

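### SAP 13 summarises oxygen saturation only as a weekly median per patient, and no planned table by arm shows the lowest reading or how many patients had low readings

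*SAP*

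**What the plan says.** Oxygen saturation has two roles. It is one of the laboratory markers of severity among the secondary endpoints (SAP 2.2 item 7 and SAP 13 item 5, both second tier). Protocol 1.3 also names it as a safety measure: "Those analytes which are also safety parameters, oxygen saturation, D-dimer and lymphocyte counts, will be followed in all patients".

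SAP 13 sets the summary. It states: "For oxygen saturation, which is measured twice daily throughout the study period, patterns will be presented visually". It then says "The median value for each subject from the preceding week will be used", with Days 2 to 8 as its example. It adds "The daily SpO2 will be the subject's median of the 14 values collected (morning and evening") and "The morning and evening SpO2 will be the median of the 7 values at that time of day". Descriptive tables are planned for Days 1, 15, 22, 29, 36, 43, 50 and 57.

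Other outputs that bear on low oxygen:

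- SAP 16.2: "Vital signs and physical findings will be shown in listings, but no calculations or study report tables will be generated". Clinically significant changes in vital signs are to be listed as adverse events. Oxygen and ventilator use is tabulated by arm, in the first tier, for hospitalised patients only.
- SAP 15: subject-level listings of vital signs. Worsening of COVID-19 counts as lack of efficacy, not as an adverse event.
- SAP 13: COVID-19 events from the adverse event records are summarised by MedDRA class, term and severity. Hospitalisation or death, and new symptoms or pneumonia, are endpoints.
- SAP 7, part A DSMB review: "Effect of treatment on oxygen saturation, C-reactive protein, lymphocyte count and D-dimer (pharmacodynamic markers"). The form of this item is not specified.

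The notes to Protocol Table 1 give the home schedule: "Oxygen saturation will be measured by patients twice daily for the first 2 weeks of study and then three times weekly", the latter covering weeks 3 and 4. The table itself has twice daily through day 15 and three times weekly through day 29.

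**The concern.** For a marker of deterioration, the useful questions are how low it went and in how many patients. A median is chosen because it ignores a minority of extreme values, and here the low values are the ones of interest. The morning and evening versions have the same property.

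Part A has about 20 patients per arm, and tolerability is judged clinically rather than by a test. At that size one or two patients with falling saturation are the information to be seen. A per-patient median, then summarised over an arm, dampens such a patient twice. Two arms that differ in the number of patients with low readings could show much the same weekly medians.

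**Working it through.** **Step 1: the plan's own figures.** Days 2 to 8 are 7 days. 7 × 2 readings = 14, and 7 for each time of day. Both match SAP 13.

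**Step 2: how many low readings the median tolerates.** With n readings, the median stays among the normal ones while the number of low readings is at most (n − 1)/2, rounded down. For n = 14 it is the mean of the 7th and 8th ordered values, so the limit is 13/2 rounded down, which is 6. This count does not depend on the saturation values. To show results, assume normal readings of 97% and low readings of 88%; neither figure comes from the documents.

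| Readings in the week | Low readings with median still 97% | One more low reading |
|---|---|---|
| 14 (complete twice-daily week) | 0 to 6 | 7 low: (88 + 97)/2 = 92.5% |
| 12 (incomplete week) | 0 to 5 | 6 low: 92.5% |
| 7 (morning or evening only) | 0 to 3 | 4 low: 88% |
| 3 (three-times-weekly schedule) | 0 to 1 | 2 low: 88% |

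Six of 14 readings equal three full days, morning and evening.

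**Step 3: with measurement noise.** Assume the same two levels, SD 1, rounded to whole percent, 40,000 simulated weeks.

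- 6 of 14 low: the median averages 95.9%, a shift of −1.1 points. It was below 92% in none of the weeks and unchanged in about 5%. The weekly mean shifts by −3.9 points (noise-free: (6 × 88 + 8 × 97)/14 = 93.1, that is 97 − 3.9).
- 7 of 14 low: average 92.5%, below 92% in about 5% of weeks.
- 8 of 14 low: average 89.1%, always below 92%.
- 1 of 3 low: average 96.4%, never below 92%.

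**Step 4: what reaches the arm summary.** One patient with 6 of 14 low readings moves the mean of 20 patients' medians by 1.1/20 = 0.055 points. A count of patients with a low reading would go from 0 of 20 to 1 of 20, or 5%.

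**Step 5: schedule against tables.**

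- SAP 13 takes twice-daily readings as given for the whole study. Under Protocol Table 1, Days 22 and 29 each rest on about three home readings.
- No home readings are scheduled for Days 36, 43 and 50. For Day 57 only the clinic visit reading is scheduled.
- Day 8, the SAP's own example, is not among the table days. Day 15 is therefore the only tabulated day that rests on 14 scheduled readings.

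**The case against.** A reader might infer that three days of low saturation leave no trace. They usually leave a small one: with ordinary noise the patient's median falls by about a point. Vital signs are also listed by subject for about 60 patients, although the SAP does not say whether home readings are in those listings.

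A reader might also infer that nothing else shows low oxygen by arm. That is too broad. Oxygen and ventilator use is tabulated by arm, hospitalisation or death is an endpoint, and clinically significant falls can enter the adverse event or COVID-19 event summaries. These are partial substitutes. The first covers hospitalised patients only, so a fall at home without admission is missed. The event summaries need an investigator to record the fall, and the Appendix 2 diary has no saturation item.

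A third inference is that the DSMB would be misled or the dose choice affected. The documents do not support it. SAP 7 does not say that the DSMB receives weekly medians, the charter is a separate document, and the same list includes serious adverse events and COVID-19 exacerbation. Pharmacodynamic parameters are expressly not used to choose the dose. Nor do the documents say that home readings stop on admission, or that readings on oxygen enter the median.

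Finally, a median is a defensible robust summary of self-measured oximetry, where single low values may be artefacts. That stands as a reason to keep it, but not as a reason to have no table of low readings.

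**Conclusion.** The point holds in a limited form. The only saturation summary that the SAP defines stays in the normal range with up to 6 of 14 low readings in a complete twice-daily week, or 1 of 3 at the three-times-weekly schedule. No planned table gives the lowest value or the number of patients with low readings by arm. The counts 6 and 1 follow from the definition of a median. The 1.1-point shift rests on the assumed levels of 97% and 88% and SD 1. The three-day figure applies only to twice-daily weeks.

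The stakes are modest. Part A is descriptive, the endpoint is second tier, and part B will have its own SAP. No test, error rate or sample size is affected. What improves is the display of a severity and safety measure in small arms, at little cost and before the rule is carried into part B.

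**What to change.** Keep the weekly median for the plots and add one descriptive table by arm:

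- each patient's lowest reading in each week, summarised by arm;
- the number and percentage of patients with any reading below 92%. This is the protocol's entry limit, used here only as an analysis cut and not as a clinical rule;
- the same count requiring two low readings, to allow for device artefact;
- readings on supplemental oxygen shown separately where recorded;
- death counted as unfavourable, as SAP 13 already does for its other binary endpoints.

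Offer this table with the oxygen saturation item in the part A DSMB review.

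In the same SAP paragraph, reconcile the stated measurement frequency, and the tables for Days 36, 43 and 50, with the protocol schedule. State how many readings each weekly value rests on. Add Day 8 to the table days.

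The cost is one table from data already collected and a few corrected lines. The downside is that single low readings may be artefacts, which is why the two-reading version belongs beside the first count.
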